20.2 Bioanalytical Methodology

The plasma samples will be analyzed for pexidartinib by using a validated method (high performance liquid chromatography (HPLC) with tandem quadrupole mass spectrometric detection) of appropriate specificity and sensitivity.

21.0 MEASUREMENT OF RESPONSE USING ^{18}F FDG PET SCANNING

Patients who consent to PET scanning should be instructed to fast for at least 6 hours (if feasible) prior to ^{18}F FDG administration to maintain basal levels of plasma glucose and insulin. They are encouraged to keep drinking water to maintain hydration and limit radiation to the urinary tract. Plasma glucose or glucometer levels will be determined before administration of ^{18}F FDG to document euglycemia.

The dose of ^{18}F FDG will be administered intravenously according to weight (0.15 mCi/kg, ranging from 3 to 16 mCi) and images will be acquired after approximately 60 minutes distribution time. Images will be obtained over the entire body from the base of the skull to mid-thigh, including brain and extremities when clinically relevant.

^{18}F FDG PET emission images will be corrected for attenuation. ^{18}F FDG PET scanning should be performed prior to biopsy collection procedure to avoid false positive results.

22.0 TUMOR AND RELATED TISSUE COLLECTION

For patients who consent to this tumor and related tissue collection procedure, paired biopsies (where applicable) will be obtained to assess the effect of pexidartinib on PD endpoints and possibly pexidartinib concentration in the tissue (PK). The tumor lesions or fluids amenable to biopsy or extraction should not be target lesions. Patients will not be excluded from the study on the basis of consenting to biopsy. For patients' safety, soft tissue lesions such as skin or subcutaneous metastases will be preferentially selected for biopsy. Liver metastases will also be eligible for biopsy provided that it is considered feasible and safe in the opinion of a staff interventional radiologist. If there is a change in dose or clinical status after C1D15, one or more additional biopsies may be obtained to assess PD and PK information, in consultation with the Sponsor. If surgical resection of the tumor is performed within 12 weeks of the last dose of study treatment, details of the surgery and its outcome should be obtained. Tumor biopsy tissue may be submitted for biomarker analysis.

Where applicable, core biopsy samples should be obtained with an 18-gauge true-cut needle core biopsy device under ultrasound or computed tomography guidance. For cutaneous or subcutaneous lesions, a punch biopsy may be performed in place of a core biopsy. The tissue samples should be submitted fresh to the surgical pathology laboratory. If feasible, one half should be fixed in 10% buffered formalin and routinely embedded in paraffin, while the other half is to be snap-frozen to -70°C .

For samples including but not limited to pleural, peritoneal, cerebrospinal, or other fluids and tissues, please refer to the Sample Handling and Logistics Manual as well as [Attachment 2](#) and [Attachment 3](#).

For patients who consent to archival tumor tissue acquisition, the sample(s) will be obtained to generate baseline or historical evidence of target relevance.

23.0 PATIENT REPORTED OUTCOME (PRO) QUESTIONNAIRES

Patients enrolled after the implementation of Amendment 8 will complete two patient reported outcome (PRO) instruments: the Western Ontario and McMaster Universities Osteoarthritis Index (WOMAC[®]) and the Numeric Rating Scale (NRS) for PVNS Symptoms questionnaire. These will be completed predose at the clinic on C1D1, C1D15, C2D1, and monthly thereafter (and at every 12-week visit after C40) while continuing study drug administration, and at the End of Study visit. In addition, these patients will complete the NRS for PVNS Symptoms questionnaire on an outpatient basis for 6 consecutive days (Day -6 to Day -1) prior to each monthly clinic visit on C1D1, C2D1, C3D1, etc. (and at every on-site visit after C40) while continuing study drug administration.

The PRO questionnaires will be used to help understand which PVNS symptoms may be most meaningful in terms of improvement for a patient, which symptoms did improve with pexidartinib, and which questions might help best detect between-group differences.

23.1 PRO Instruments

Western Ontario and McMaster Universities Osteoarthritis Index (WOMAC®)

The WOMAC ([Attachment 7](#)) is a self-administered 24-item instrument assessing pain, stiffness and difficulty performing daily activities. The WOMAC is focused on assessing issues associated with lower extremity conditions, mainly the knee and hip. All items include a 0–10 point NRS scale; the scale for the pain items (5 items) is 0 “no pain” to 10 “extreme pain”, the scale for the stiffness items (2) is 0 “no stiffness” to 10 “extreme stiffness”, and the scale for the difficulty performing daily activity items (17) is 0 “no difficulty” to 10 “extreme difficulty.”

Numeric Rating Scale (NRS) for PVNS Symptoms

The NRS for PVNS Symptoms instrument is a 5-item self-administered questionnaire to assess the “worst” of each of the symptoms pain, swelling, stiffness, instability and limited motion in the last 24 hours ([Attachment 6](#)). A 0–10 NRS is provided for each symptom. For pain, 0 indicates “no pain” and 10 indicates “pain as bad as you can imagine,” For the other four symptoms, 0 indicates “no (*symptom*)” and 10 indicates “(*symptom*) worst imaginable”, e.g., “swelling – worst imaginable.”

24.0 STATISTICAL ANALYSIS

24.1 Safety Analysis

All patients in all cohorts who received study medication will be considered evaluable for safety regardless of their duration of treatment.

The objective of the dose escalation is to determine a dose of pexidartinib for which the rate of DLTs is less than 33%. Safety variables to be analyzed are AEs, laboratory test results (hematology, clinical chemistry, coagulation parameters, and urinalysis), ECG, and vital signs. Adverse event terms recorded on the CRFs will be mapped to preferred terms using the Medical Dictionary for Drug Regulatory Activities (MedDRA®) version 7.1 or higher. All AEs will be summarized for each dose group according to the system organ class and preferred term within the organ class. Adverse events will be tallied for overall frequency (number and percentage of subjects), worst reported severity, and relationship to study drug for each preferred term per subject. Serious adverse events will be similarly summarized. Listings of deaths, SAEs, and AEs leading to early termination of study treatment or premature withdrawal from study will also be provided. In addition, all events meeting the criteria of a DLT will be tabulated as a separate listing by subject and dose group. Laboratory variables will be examined using mean change in value from baseline to scheduled time points for each pexidartinib dose group. Laboratory values

will also be categorized according to their CTCAE (version 4) toxicity grade and tabulated by worst on-study toxicity grade and pexidartinib dose group. The baseline value of a variable is defined as the last value obtained on or before the date and time of the first pexidartinib dose. Concomitant medications will also be summarized.

ECG/QT Analysis:

All ECG information will be listed by patient, including change from baseline for numeric ECG parameters (based on means of the triplicate assessments). Summaries by time-point will be provided for absolute and change from baseline numeric ECG parameters (including categorical summaries for QTc absolute and change from baseline). Plots of mean ECG data and their change from baseline over time will be provided. For each of the time points, the available triplicate QTc values will be averaged for all analyses.

The primary study variable for the QT evaluation will be the study specifically corrected QT interval (QTcS or QTcF or QTcB) change from baseline. The correction formulae for QTc will be estimated based on linear or non-linear regression of predose QT interval data and RR data.

In addition, change from baseline for other ECG variables (QT, RR, heart rate, PR, QRS) will be summarized.

Corrected mean changes from baseline in QTc together with one-sided upper 95% confidence intervals will be derived for each timepoint to interpret the effect of pexidartinib on the QT interval.

The following criteria on baseline measurements will be considered in the analysis of the QT interval. Patients who fall within these criteria may bias the interpretation of pexidartinib effect on QT interval. Data from these patients may be analyzed separately from the general patient population.

- Heart rate (HR) greater than 90 or less than 45 beats per minute
- Sustained systolic blood pressure measurements <90 or >140 mmHg or diastolic blood pressure measurements <50 or >90 mmHg at screening or Day -1
- Any concomitant medications that prolong QT/QTcF interval
- History and/or family history of congenital long QT syndrome or sudden death
- Clinically significant abnormal ECG (e.g., marked QT/QTcF prolongation)
- More than 30 msec difference in two extreme, highest and lowest reads of any baseline QTcF at a specific time point
- Short QTcF (<300 msec) at screening or baseline
- Screening or baseline ECG evidence of atrial fibrillation, atrial flutter, complete right or left bundle branch block, WPW-syndrome, or cardiac pacemaker

- QRS and/or T-wave judged to be unfavorable for a consistently accurate QT measurement at baseline (e.g., indistinct QRS onset, low amplitude T-wave, merged T- and U-waves, prominent U-waves)

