Study Procedures	
After providing informed consent, patients will undergo screening for eligibility to participate in the study. Screening will start within 21 days prior to dosing with the exception of tumor burden assessment (e.g., CT scan) which may have been performed within 28 days.
 
A cycle of dosing is defined as 28 days. In each dose escalation cohort, patients will receive their assigned dose of pexidartinib on the morning of Cycle 1 Day 1 (C1D1) and will remain in the outpatient clinic for 8 hours for observation and pharmacokinetic (PK) sampling. For QD dosing, PK samples will be collected prior to dosing and 0.5, 1, 2, 4, and 8 hours following dosing. The initial dosing regimen of pexidartinib will be once daily by oral administration. A twice daily dosing regimen may be used in subsequent cohorts, depending on the PK data obtained from once-daily dosing in the first cohort. For BID dosing, PK samples will be obtained predose (AM) and 1, 2, 4, 7 hours postdose on C1D1. The second dose will then be administered, and a 1 hr post dose sample will be obtained (8 hours after the first dose). Patients will return to the clinic on the morning of C1D2 and C1D8 prior to dosing on that day for evaluation and blood draw to obtain the predose PK time-point (approximately 12 hours after the previous evening dose for a BID dosing regimen). Patients will continue to dose pexidartinib once or twice daily and return to the clinic for evaluation on C1D8. On C1D15 and C1D16 (± 2 days), blood samples will be obtained once again for measurement of pexidartinib PK, using the same sampling times as on C1D1 and C1D2. Patients will return to the clinic on C2D1 for evaluation. If pexidartinib has been well tolerated and there has been no clinical evidence of disease progression, continued dosing will be permitted. Patients with solid tumors will be monitored for response and disease progression with tumor burden assessments every two months.
 
In selected cohorts, 3–6 patients will be treated with a pexidartinib dose of 100 mg QD during a one-week run-in period before increasing to the full dose for that cohort, in order to profile the pharmacodynamic (PD) dose response activity of pexidartinib at doses below 300 mg QD. Similarly, 3–6 patients will be treated with a pexidartinib dose of 200 mg QD during a one-week run-in period. After baseline predose blood is obtained on C1D(-7), the first dose of 100 mg or 200 mg will be administered, and PK samples will be obtained. Patients will return to the clinic the following AM (C1D(-6)) and 2 days later (C1D(-4)) for blood draws for PK and the PD biomarkers. They will then return for C1D1 for initiation of dosing at the full dose for that cohort.

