Chemistry, hematology, urinalysis		X		X ⁵	X ⁵	X ⁵	X ⁵ (no urinalysis)	X	
ECG		X		X				X	
Vital Signs		X	X	X	X	X	X (unless remote)	X	
Plasma for PK ⁶			X	X	X	X			
Pregnancy Test ⁷		X						X	
ECOG Performance Status Assessment		X			X	X		X	
WOMAC Questionnaire ⁸			X	X	X	X	X (unless remote)	X	
Numeric Rating Scale (NRS) for PVNS Symptoms Questionnaire to Patient ⁸			X	X	X	X	X (unless remote)	X	
Dispense Numeric Rating Scale (NRS) for PVNS Symptoms Questionnaire for Outpatient Completion ⁹		X		X	X	X	X (unless remote)		
Serum and Urine for Biomarker Assessment ¹⁰			X		X				
Radiographic Assessment of Tumor Burden ¹¹		X				X	X (every 6 months)	X	X
Test Article Compliance			X	X	X	X	X (unless remote)	X	
Concomitant Medications		X	X	X	X	X	X	X	
Adverse Events ¹²			X	X	X	X	X	X	
Collection of surgical data ¹³								X	X

C = cycle; D = day; CxDx = Cycle x, Day x; LD = last dose; wk = week

- ¹ Screening window for radiographic assessment of tumor burden is 4 weeks.
- ² If well tolerated and no tumor progression; clinic visits, laboratories at 1-month intervals with radiographic assessment performed every two cycles. Radiographic assessment of tumor status can be performed every four cycles in patients who complete 14 cycles of treatment (i.e., reached Cycle 15 visit) and have Cycle 13 and Cycle 15 MRI scans that indicate SD or better per local RECIST v1.1 reading. For patients beyond Cycle 40, clinic visits will transition to every 12 weeks/3 cycles (remote serum chemistry and hematology as well as a telephone check-in for AEs and con meds and to review remote safety laboratory data may be performed in lieu of an on-site visit for subjects without ongoing Grade 2 or greater related adverse events; regular procedures not performed remotely include Weight, PE, Vitals, WOMAC, NRS, and IP compliance), with on-site visit and radiographic assessments performed every 24 weeks/6 cycles.
- ³ End of Study or early withdrawal procedures should be completed 7-30 days after the last dose of study drug (or on the date of last dose of study drug for all subjects that enroll in the phase 4 continuation study) and prior to the initiation of any new anti-cancer therapy. If patient is starting commercially available drug then the end of study visit should be conducted before that transition.

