After the initial 4 weeks of dosing, all patients will be able to continue receiving pexidartinib at their assigned dose provided they meet the criteria described in [Section 13.8](#). Patients will return for clinical evaluation every 28 days and will have radiographic assessments (solid tumors) for response and progression after every two months of drug administration.

Extension Cohorts:

At the recommended Phase 2 dose of 1000 mg/day, a total of six Extension cohorts will be enrolled and followed for safety and tumor response as assessed by CT scan every 8 weeks (or, beyond Cycle 40, every 24 weeks). Participants will remain on treatment until tumor progression, as long as there are no unacceptable toxicities.

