18.0 SAFETY EVALUATION

Routine safety and tolerability will be evaluated from the results of reported signs and symptoms, scheduled physical examinations, vital sign measurements, 12-lead ECGs (including QTc intervals), and clinical laboratory test results.

Safety data will be reviewed by the investigator and the medical monitor. Safety of pexidartinib will be established after 28 days of dosing at the previous dosage group before the next higher dose is initiated.

More frequent safety evaluations may be performed if clinically indicated or at the discretion of the investigator. All AEs will be recorded from the time the patient receives the first dose of study drug until the patient's End of Study visit.

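### The cumulative AE and SAE tables by dose group in Section 24.1 ignore time on drug, so differences between dose groups may reflect length of exposure rather than dose

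*Combined protocol and SAP*

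**What the plan says.** Section 24.1 sets the safety population without regard to time on drug: "All patients in all cohorts who received study medication will be considered evaluable for safety regardless of their duration of treatment". It then states "All AEs will be summarized for each dose group", arranged by system organ class and preferred term, and gives the measure: "Adverse events will be tallied for overall frequency (number and percentage of subjects), worst reported severity, and relationship to study drug". SAEs get the same treatment. Laboratory toxicity grades are also tabulated by dose group as the worst grade on study.

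The collection window follows each patient's time on study. Section 18.0 says "All AEs will be recorded from the time the patient receives the first dose of study drug", and collection ends at the End of Study visit.

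That time varies widely by design:
- Section 9.4 gives escalation patients 4 weeks at their dose and then offers continued dosing.
- Section 9.5 keeps extension patients on drug until progression or toxicity.
- Footnote 2 of the extension flow chart provides for very long treatment: "For patients beyond Cycle 40, clinic visits will transition to every 12 weeks/3 cycles".
- Section 9.1 places all extension patients at one starting dose: "At the recommended Phase 2 dose of 1000 mg/day, a total of six Extension cohorts will be enrolled".

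Some safety output does respect time. DLTs are judged over the first 28 days (Section 16.4) and listed by subject and dose group. Laboratory means and ECGs are summarised by time point. The text has no exposure summary, patient-time rate, time-to-first-AE estimate or AE table by cycle.

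**The concern.** The percentage of patients with at least one event rises with follow-up, even if the risk per month is constant and does not depend on dose. A table by dose group invites a comparison of doses. If one dose group holds patients treated for years and another holds patients who left after a scan or two, the first will show the higher percentages whatever the drug does. The reverse is also possible: a dose with a truly higher risk can look safer because its patients were followed briefly.

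The explicit schedule beyond Cycle 40 belongs to the extension cohorts, so long follow-up is likely to concentrate at 1000 mg/day. Escalation patients may also continue with no fixed end, however, and the documents give no actual durations. The imbalance is possible by design, but its size is unknown.

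At stake is how the cumulative AE and SAE tables are read. Section 24.6 names safety as the study's primary objective, and Section 8.1 does so for the escalation phase.

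**Working it through.** The plan states no AE rate and no exposure time, so there is no figure to reproduce. The check asks how far crude percentages can differ when the risk is the same in every dose group.

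**Inputs from the documents.** Cycle length: "A cycle of dosing is defined as 28 days". Long exposure: beyond Cycle 40, that is 40 × 28 = 1,120 days, about 3.1 years. Measure: the percentage of subjects with the event at any time on study.

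**Assumed inputs (not in the documents).** A constant first-event hazard h per cycle, equal in all groups: 0.02, range 0.01 to 0.05. Exponential time on drug with median 2, 4, 12 or 24 cycles, capped at 40 cycles.

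**Formulas.** The drop-out hazard is m = ln 2 / median.
- Crude percentage = h/(h+m) × [1 − exp(−40(h+m))].
- Mean cycles at risk = [1 − exp(−40(h+m))]/(h+m).

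**Worked case, h = 0.02.**
- Median 2: m = 0.3466, h+m = 0.3666. Crude = 0.02/0.3666 × [1 − exp(−14.66)] = 5.5%. Cycles at risk = 2.73.
- Median 24: m = 0.0289, h+m = 0.0489. Crude = 0.02/0.0489 × [1 − exp(−1.955)] = 0.409 × 0.858 = 35.1%. Cycles at risk = 17.56.

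**Crude percentage by median time on drug.**

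| h per cycle | 2 cycles | 4 cycles | 12 cycles | 24 cycles | Ratio, 24 vs 2 |
|---|---|---|---|---|---|
| 0.01 | 2.8% | 5.5% | 13.8% | 20.3% | 7.2 |
| 0.02 | 5.5% | 10.3% | 24.6% | 35.1% | 6.4 |
| 0.05 | 12.6% | 22.4% | 45.8% | 60.7% | 4.8 |

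The risk per cycle is identical along each row, so the whole difference comes from follow-up.

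**Reversal.** With fixed follow-up, crude = 1 − exp(−ht). A dose with hazard 0.04 followed for 2 cycles shows 1 − exp(−0.08) = 7.7%. A dose with half that hazard followed for 12 cycles shows 1 − exp(−0.24) = 21.3%.

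**Two remedies on the same data (h = 0.02).**
- Fixed Cycle 1 window: 1 − exp(−0.02) = 2.0% in every group, if all complete the cycle.
- Patient-time rate: 0.055/2.73 and 0.351/17.56 both give 0.02 per cycle.

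**Where the patient-time rate fails.** Suppose 20% of patients have an event midway through Cycle 1 and no events occur later. The crude figure is 20% whether follow-up is 2 or 40 cycles, which is correct.
- 2 cycles: 0.2/(0.2 × 0.5 + 0.8 × 2) = 0.2/1.7 = 11.8 per 100 patient-cycles.
- 40 cycles: 0.2/(0.2 × 0.5 + 0.8 × 40) = 0.2/32.1 = 0.62 per 100 patient-cycles.

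That is a 19-fold artefact in the opposite direction, so the rate cannot be the main comparison.

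**The case against.** The strongest reply is that no dose decision rests on these tables. Escalation and the MTD use DLTs in a fixed 28-day window (Section 16.4), and the same section treats Cycle 1 as the main safety period. The extension dose is already set in the text. Section 24.5 calls the analyses descriptive, and Section 8.1 makes clinical benefit the primary objective of the extension. Escalation levels hold only 3 to 6 patients, so rates there say little: 3 patients followed for an assumed 2 months give 6 patient-months, and one event then has an exact Poisson 95% interval of 0.4 to 93 per 100 patient-months. All of this stands. It confines the point to interpretation and shapes the remedy, but it does not make the by-dose percentages comparable.

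A reader might infer more than the documents support:
- **That crude percentages dilute early severe toxicity in short-exposure patients.** They do not. Under Section 24.1 an early event counts in full as one patient, however short the exposure. Patient-time rates are what shrink early-onset events when follow-up is long.
- **That the distortion is as large as a comparison of fixed exposure lengths suggests.** Setting 2 cycles against 40 gives 3.9% vs 55.1% at h = 0.02, and about 9-fold (h = 0.05: 9.5% vs 86.5%) to 17-fold (h = 0.01: 2.0% vs 33.0%) over the range. This treats every patient in a group as having the same exposure. A dose group is a mixture, and nothing in the documents supports such an extreme contrast.
- **That the six extension cohorts are known to differ greatly in treatment length.** The documents give open-ended dosing rules and no durations by cohort.

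**Conclusion.** The point holds in a limited form. The cumulative AE and SAE tables by dose group mix dose with time on drug, and no other planned output separates the two for AEs in general. With equal risk, the distortion is about 5- to 7-fold for median time on drug of 2 versus 24 cycles. That size rests on an assumed constant hazard of 0.01 to 0.05 per cycle and on assumed durations; the real imbalance cannot be known from the documents. The DLT-based escalation rule and the MTD are not called into question. The change is worth making because safety is a primary objective and the missing information can be derived from dosing records and AE onset dates.

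**What to change.** Keep the crude tables and add to Section 24.1:

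1. A summary of exposure duration by dose group and, within 1000 mg/day, by extension cohort.
2. As the main dose comparison, percentages of patients with any AE, with a Grade 3 or higher AE and with an SAE, limited to Cycle 1 and to Cycles 1-2, by assigned starting dose. Show how many patients completed each window.
3. As secondary output, first-event rates per patient-time with exact Poisson confidence intervals for Grade 3 or higher AEs, SAEs and liver AEs, mainly for the 1000 mg/day group and its cohorts. Add a note that these rates assume a roughly constant hazard and understate early-onset events in long-exposure groups.

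State that dose group means assigned dose in these tables. Section 24.1 does not say whether it means assigned dose or dose at onset, although Section 14.7 allows reductions in 200 mg/day steps and Section 9.1 describes run-in weeks at 100 or 200 mg. The text should also say where run-in events are counted.

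The cost is SAP wording and a few extra tables; no visit, procedure or sample size changes. The downside is longer output and very wide intervals wherever rates are shown for escalation levels of 3 to 6 patients.

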DB = direct bilirubin; GGT = gamma-glutamyl transferase; TB = total bilirubin; ULN = upper limit of normal

^a Confirm ALP elevations as liver isozyme fraction.

Dose interruptions for Grade 2 non-hematologic toxicity for up to 1 week can be implemented at the discretion of the treating physician to manage intolerable or clinically significant toxicity. No dose reduction is required when resuming treatment.

Liver enzyme abnormalities, including increased transaminase values, have occurred with pexidartinib and should also be managed as described in [Table 4](#).

Re-challenge with a reduced dose of pexidartinib may result in a recurrence of increased serum transaminases, bilirubin, or ALP. Monitor liver tests weekly for the first month after re-challenge.

Table 4: Additional Liver Evaluation

Evaluation	Comments
Increase frequency of testing liver chemistries to twice per week (if Grade 3+), including INR, and continue until liver chemistries have stabilized, and then reduce to weekly until liver chemistries return to normal or baseline.	Investigational treatment may be started after liver function tests recover to Grade 0 to 1 or baseline level, and in consultation with Medical Monitor.
Detailed history focusing on medications and substances used: alcohol, change in medication dosages, new medications added, attention to use of acetaminophen, OTC medication use, and recreational drug use. Check for change in diet or use of dietary supplements, with particular attention to dose and duration of any herbal product.	Suspect medications will be discontinued or substituted for if possible.
Detailed medical history and physical examination seeking new abnormalities.	Evaluate abnormalities found.
Full serological evaluation for hepatitis A, B, C, and E (IgG and IgM). Check for autoimmune hepatitis with serological laboratory studies.	If viral hepatitis or autoimmune hepatitis suggested, have patient evaluated by hepatologist.
Liver ultrasound performed to evaluate liver and biliary tree.	Evaluate any abnormalities found.
Check history for exposure to chemical agents.	Remove chemical exposure and have patient seen by hepatologist.
Obtain hepatology consult if liver function continues to rise beyond 14 days.	Contact Medical Monitor.
We request that cases be discussed with the Medical Monitor as defined in the protocol whenever investigational product is being held for liver function test abnormality.	

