Ig = Immunoglobulin; INR = international normalized ratio; OTC = over-the-counter

For suspected cases of cholestatic liver injury (e.g., aminotransferase increase concurrent with hyperbilirubinemia, or liver biopsy suggesting cholestasis and/or ductopenia), patients will be followed to assess long-term outcome. Additional diagnostic and follow-up procedures might be implemented as appropriate to fully assess the event.

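### Section 24.1 summarises liver tests one analyte at a time, with no by-patient laboratory listing, so no planned output counts patients whose ALT/AST and bilirubin rise together

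*Combined protocol and SAP*

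**What the plan says.** Section 24.1 gives laboratory data two treatments. One is mean change: "Laboratory variables will be examined using mean change in value from baseline to scheduled time points for each pexidartinib dose group". The other has values "categorized according to their CTCAE (version 4) toxicity grade and tabulated by worst on-study toxicity grade", again by dose group.

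The by-patient safety outputs are then named. "Listings of deaths, SAEs, and AEs leading to early termination of study treatment or premature withdrawal from study will also be provided". Dose-limiting toxicities have an output of their own, where "all events meeting the criteria of a DLT will be tabulated as a separate listing by subject and dose group". For ECG the plan goes further: "All ECG information will be listed by patient, including change from baseline for numeric ECG parameters". There is no matching sentence for laboratory data. Sections 24.4 and 24.5 add listings by dose of pharmacodynamic and patient-reported data, which do not cover safety chemistry.

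On the liver, Section 14.7 (extension cohorts) states: "Liver enzyme abnormalities, including increased transaminase values, have occurred with pexidartinib". After Table 4 it turns to "suspected cases of cholestatic liver injury (e.g., aminotransferase increase concurrent with hyperbilirubinemia", with a suggestive biopsy as the other example, and says such "patients will be followed to assess long-term outcome". Table 3 in the same section sets dosing actions for ALT/AST and for bilirubin in separate rows.

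**The concern.** The protocol treats the combination of raised aminotransferases and raised bilirubin as a pattern in its own right and sets up extended follow-up for it. The analysis section has no output that identifies it. A report that followed Section 24.1 would give the frequency of ALT elevation, of AST elevation and of bilirubin elevation, each by dose group, without saying how many patients had both kinds or whether they occurred at the same time. An isolated transaminase rise and a combined rise are clinically different findings, and separate tables cannot tell them apart.

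This matters because safety is a primary objective of dose escalation (Section 8.1), every treated patient is evaluable for safety (Section 24.1), and the protocol already records liver enzyme abnormalities with this drug.

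**Working it through.** The plan states no figure on this point, so there is nothing to reproduce. The check has three steps.

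**1. What each planned output can show**

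- *Mean change from baseline (24.1).* An average per analyte at scheduled visits, with no patient count. Table 3 moves to weekly or twice-weekly liver tests once values rise, so a peak can fall between scheduled visits.
- *Worst on-study grade (24.1).* A patient count per analyte and dose group. It links neither analytes nor dates. ALT and AST are themselves separate analytes, so even the number with either one raised is not supplied directly.
- *AE tallies (24.1).* Counts by preferred term. Section 26.1 asks for a clinically significant laboratory abnormality to be entered as one diagnosis, so the tally counts the term the site chose, not the paired values.
- *Listings of deaths, SAEs, AEs leading to termination or withdrawal, and DLTs (24.1).* Individual events, none selected by concurrent liver values.
- *ECG listing (24.1).* By patient, but not laboratory data.

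**2. Whether the joint count can be recovered from separate counts**

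In a dose group of n patients, let a have ALT or AST raised at some time and b have bilirubin raised at some time. The number with both, at any time, lies between

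max(0, a + b − n) and min(a, b).

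The two ends meet only if one count is zero or one count equals n. Otherwise the tables leave the number open. How open depends on the dose group. Dose levels hold 3 to 6 patients (Section 24.6), so the range can be tight. With assumed counts a = 5 and b = 3 in a level of n = 6, the lower end is 5 + 3 − 6 = 2 and the upper end is 3. Even then, 2 to 3 counts patients with both elevations at some time. Worst grades carry no dates, so the number with concurrent elevations could still be anything from 0 to 3.

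The values of a and b here are assumed only to show the mechanics. The documents give no liver-event rates. Section 24.1 tabulates by dose group rather than by extension cohort, and the extension cohorts share one assigned regimen of 1000 mg/day. No estimate of the gap's size follows from the text.

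**3. Which paired cases surface individually**

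- *Any cohort:* a case judged serious is listed as an SAE, and Section 26.1 resolves doubt in favour of SAE status.
- *Dose escalation, first 28 days:* Grade 3 or 4 elevations meet the DLT definition in Section 16.4 and are listed.
- *Extension cohorts:* Table 3 requires permanent discontinuation for total bilirubin ≥2 × ULN, direct bilirubin >1.5 × ULN, ALT/AST >10 × ULN, ALP with GGT both >2 × ULN, or no recovery in 4 weeks. An abnormality that changes dosing must be recorded as an AE (Section 26.1), so these should reach the early-termination listing.

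Unless judged an SAE, two groups can miss every by-patient listing:

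- Extension patients with ALT/AST >3 to 10 × ULN and total bilirubin >ULN to <2 × ULN who recover, have an alternate cause for the bilirubin confirmed, and resume. Interruptions over 3 weeks also need medical monitor approval to continue.
- Dose-escalation patients with paired Grade 2 elevations at any time, or Grade 3 or higher after Day 28, who continue or are re-challenged under Section 13.9. The follow-up sentence in Section 14.7 does not apply to them.

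**The case against.** The strongest reply is that the omission changes little. Most of it stands.

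- Section 24.1 is not a complete catalogue of outputs. It names vital signs as a variable to be analysed and then gives no method for them, and Section 24.5 says only that analyses are broadly descriptive. The text supports saying that the paired output is not specified. It does not show that the sponsor meant to exclude it.
- The serious cases mostly surface. A reader might infer that dangerous liver injury could go unreported. The documents do not support that: the SAE, DLT and Table 3 rules catch most serious pairs, and the unlisted extension group is narrow, with lower bilirubin and a confirmed alternate cause.
- Case-level review exists. Table 4 asks for discussion with the Medical Monitor whenever drug is held for liver tests, and Section 13.9 requires the Sponsor to be told of drug-related Grade 2 toxicity.
- A unifying liver diagnosis would be counted in the AE tallies.
- No decision depends on the count. The MTD rests on DLTs (Section 16.4) and the extension rule on clinical benefit in at least 2 patients (Section 24.6). A reader might infer a threat to dose selection or to the go/no-go rule, and there is none.
- The values are collected, so the count could be produced later without changing the design.

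What the reply does not remove is the gap itself. Appearing in a listing for another reason is not a count of the pattern, case review is not an analysis output, and an AE term need not show that two analytes rose together.

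**Conclusion.** The point holds as a modest reporting gap that should be closed. As specified, Section 24.1 has no output that counts patients with concurrent ALT/AST and bilirubin elevation, and no by-patient laboratory listing from which a reader could construct the count. Section 14.7 singles that pattern out for the extension cohorts only; for dose escalation the argument rests on safety being a primary objective.

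Its size cannot be estimated from the documents. A reader might want to attach a percentage of missed cases, but any such figure would rest wholly on assumed rates, and the number of cases absent from every listing could be zero. The conclusion depends on reading Section 24 as the analysis plan, which is reasonable because this is a combined protocol and SAP and the text supplied points to no separate one.

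**What to change.** Add to Section 24.1, for all cohorts, by dose group and extension cohort:

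- **(a)** a per-patient plot or table of peak ALT or AST (× ULN) against peak total bilirubin (× ULN), using scheduled and unscheduled post-baseline values;
- **(b)** a count and by-patient listing of patients with ALT or AST >3 × ULN together with total bilirubin >ULN, and separately with total bilirubin ≥2 × ULN, within a fixed window. Thirty days is one possibility; that value is an assumption, and the sponsor should set the window.

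The ALT/AST cut is the protocol's own trigger for close follow-up (Attachment 1), and the bilirubin cuts come from Table 3. Both bilirubin levels are needed: in the extension cohorts ≥2 × ULN already forces discontinuation, so the lower cut is the one that finds patients who resumed.

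The listing should show baseline values, ALP, GGT where available, liver-metastasis status, action taken and outcome, including any collected under Section 14.7. Baseline and metastasis status matter because inclusion criterion 9 admits AST/ALT up to <5 × ULN with liver metastases and sets no bilirubin limit.

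The cost is one extra table or plot, one listing and a little programming. ALT, AST, total and direct bilirubin and ALP are in the routine chemistry panel (Attachment 1), so no added patient procedure is needed. GGT is a reflex test and will be incomplete.
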